## 9.2 Demographics and Subject Disposition

Subject disposition will be listed. The demographic variables age, sex, race, ethnicity, country of enrolment, site ID, body weight, height and body mass index will be summarized and listed.

## 9.3 Pharmacokinetic Assessment

### 9.3.1 Pharmacokinetic Analysis

PK parameter estimates will be determined using non-compartmental procedures in validated software program (Phoenix WinNonlin Version 6.4 or later). For the calculation of the PK parameter estimates, the samples collected at predose of Days 3 and 5 will also be used as 48 h postdose samples of the Day 1 and 3 PK profiles, respectively.

Plasma concentrations of lasmiditan (LY573144) will be used to determine the following PK parameters, when possible:

Parameter	Units	Definition
$C_{\max}$	ng/mL	maximum observed drug concentration
$t_{\max}$	h	time of maximum observed drug concentration
$AUC(0-\infty)$	ng.h/mL	area under the concentration versus time curve from time zero to infinity
$AUC(0-t_{\text{last}})$	ng.h/mL	area under the concentration versus time curve from time zero to time $t$ , where $t$ is the last time point with a measurable concentration
$\%AUC(t_{\text{last}}-\infty)$	%	percentage of $AUC(0-\infty)$ extrapolated
$t_{1/2}$	h	half-life associated with the terminal rate constant ( $\lambda_z$ ) in non-compartmental analysis
CL/F	L/h	apparent total body clearance of drug calculated after extra-vascular administration
$V_z/F$	L	apparent volume of distribution during the terminal phase after extra-vascular administration
$V_{\text{SS}}/F$	L	apparent volume of distribution at steady state after extra-vascular administration

Additional PK parameters may be calculated, as appropriate. The software and version used for the final analyses will be specified in the CSR. Any exceptions or special handling of data will be clearly documented within the final study report.

Formatting of tables, figures and abbreviations will follow the Eli Lilly Global PK/PD/TS Tool: NON-COMPARTMENTAL PHARMACOKINETIC STYLE GUIDE. The version of the tool effective at the time of PK analysis will be followed.

## General PK Parameter Rules

- Actual sampling times will be used in the final analyses of individual PK parameters, except for non-bolus pre-dose sampling times which will be set to zero.
- $C_{max}$  and  $t_{max}$  will be reported from observed values. If  $C_{max}$  occurs at more than one time point,  $t_{max}$  will be assigned to the first occurrence of  $C_{max}$ .
- AUC parameters will be calculated using a combination of the linear and logarithmic trapezoidal methods (linear-log trapezoidal rule). The linear trapezoidal method will be applied up to  $t_{max}$  and then the logarithmic trapezoidal method will be used after  $t_{max}$ . The minimum requirement for the calculation of AUC will be the inclusion of at least three consecutive plasma concentrations above the lower limit of quantification (LLOQ), with at least one of these concentrations following  $C_{max}$ .
- AUC(0-∞) values where the percentage of the total area extrapolated is more than 20% will be flagged. Any AUC(0-∞) value excluded from summary statistics will be noted in the footnote of the summary table.
- Half-life ( $t_{1/2}$ ) will be calculated, when appropriate, based on the apparent terminal log-linear portion of the concentration-time curve. The start of the terminal elimination phase for each subject will be defined by visual inspection and generally will be the first point at which there is no systematic deviation from the log-linear decline in plasma concentrations. Half-life will only be calculated when a reliable estimate for this parameter can be obtained comprising of at least 3 data points. If  $t_{1/2}$  is estimated over a time window of less than 2 half-lives, the values will be flagged in the data listings. Any  $t_{1/2}$  value excluded from summary statistics will be documented in the footnote of the summary table.
- A uniform weighting scheme will be used in the regression analysis of the terminal log-linear portion of the concentration-time curve.
- The parameters based on predicted last measurable drug concentration ( $C_{last}$ ) will be reported.

## Individual PK Parameter Rules

- Only quantifiable concentrations will be used to calculate PK parameters with the exception of special handling of certain concentrations reported below the lower limit of quantitation (BQL). Plasma concentrations reported as BQL will be set to a value of zero when all of the following conditions are met:
  - The compound is non-endogenous.
  - The samples are from the initial dose period for a subject or from a subsequent dose period following a suitable wash-out period.

- The time points occur before the first quantifiable concentration.
- All other BQL concentrations that do not meet the above criteria will be set to missing.
- Also, where two or more consecutive concentrations are BQL towards the end of a profile, the profile will be deemed to have terminated and therefore any further quantifiable concentrations will be set to missing for the calculation of the PK parameters unless it is considered to be a true characteristic of the profile of the drug.

### **Individual Concentration vs. Time Profiles**

- Individual concentrations will be plotted utilizing actual sampling times.
- The terminal point selections will be indicated on a semi-logarithmic plot.

### **Average Concentration vs. Time Profiles**

- The average concentration profiles will be graphed using scheduled (nominal) sampling times.
- The average concentration profiles will be graphed using arithmetic average concentrations.
- The pre-dose average concentration for single-dose data from non-endogenous compounds will be set to zero. Otherwise, only quantifiable concentrations will be used to calculate average concentrations.
- Concentrations at a sampling time exceeding the sampling time window specified in the protocol, or  $\pm 10\%$ , will be excluded from the average concentration profiles.
- Concentrations excluded from the mean calculation will be documented in the final study report.
- A concentration average will be plotted for a given sampling time only if 2/3 of the individual data at the time point have quantifiable measurements that are within the sampling time window specified in the protocol or  $\pm 10\%$ . An average concentration estimated with less than 2/3 but more than 3 data points may be displayed on the mean concentration plot if determined to be appropriate and will be documented within the final study report.

### **Treatment of Outliers during Pharmacokinetic Analysis**

Application of this procedure to all PK analyses is not a requirement. Rather, this procedure provides justification for exclusion of data when scientifically appropriate. This procedure describes the methodology for identifying an individual value as an outlier for potential exclusion, but does not require that the value be excluded from analysis. The following methodology will not be used to exclude complete profiles from analysis.

### Data within an Individual Profile

A value within an individual profile may be excluded from analysis if any of the following criteria are met:

- For PK profiles during single dosing of non-endogenous compounds, the concentration in a pre-dose sample is quantifiable.
- For any questionable datum that does not satisfy the above criteria, the profile will be evaluated and results reported with and without the suspected datum.

### Data between Individual Profiles

1. If  $n < 6$ , then the dataset is too small to conduct a reliable range test. Data will be analyzed with and without the atypical value, and both sets of results will be reported.
2. If  $n \geq 6$ , then an objective outlier test will be used to compare the atypical value to other values included in that calculation:
  - a. Transform all values in the calculation to the logarithmic domain.
  - b. Find the most extreme value from the arithmetic mean of the log transformed values and exclude that value from the dataset.
  - c. Calculate the lower and upper bounds of the range defined by the arithmetic mean  $\pm 3 \times \text{SD}$  of the remaining log-transformed values.
  - d. If the extreme value is within the range of arithmetic mean  $\pm 3 \times \text{SD}$ , then it is not an outlier and will be retained in the dataset.
  - e. If the extreme value is outside the range of arithmetic mean  $\pm 3 \times \text{SD}$ , then it is an outlier and will be excluded from analysis.

If the remaining dataset contains another atypical datum suspected to be an outlier and  $n \geq 6$  following the exclusion, then repeat step 2 above. This evaluation may be repeated as many times as necessary, excluding only one suspected outlier in each iteration, until all data remaining in the dataset fall within the range of arithmetic mean  $\pm 3 \times \text{SD}$  of the log-transformed values.

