### Reporting of Excluded Values

Individual values excluded as outliers will be documented in the final report. Approval of the final report will connote approval of the exclusion.

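### Does the PK outlier rule need rewording because step 2e makes exclusion mandatory and asks for no with-and-without summary at n of 6 or more?

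*SAP*

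**What the plan says.** The rule sits in SAP 9.3.1 under four sub-headings.

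- **Treatment of Outliers during Pharmacokinetic Analysis** introduces it. The procedure need not be applied to every PK analysis, "this procedure provides justification for exclusion of data when scientifically appropriate", and the method for identifying an outlier "does not require that the value be excluded from analysis". It may not be used to remove complete profiles.
- **Data within an Individual Profile** allows exclusion of a value that meets the listed criterion (a quantifiable pre-dose concentration in single dosing). For a questionable value that does not meet it, "the profile will be evaluated and results reported with and without the suspected datum".
- **Data between Individual Profiles** splits by n. Below six values a range test is considered unreliable, so "Data will be analyzed with and without the atypical value, and both sets of results will be reported". From six values upward, the most extreme log value is compared with the mean ± 3 SD of the others. If it falls outside, "then it is an outlier and will be excluded from analysis". The test may be repeated: "If the remaining dataset contains another atypical datum suspected to be an outlier" and at least six values remain, step 2 is run again.
- **Reporting of Excluded Values**: "Individual values excluded as outliers will be documented in the final report".

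Elsewhere, 9.3.1 adds that "Any exceptions or special handling of data will be clearly documented within the final study report". Its General PK Parameter Rules call for a footnote when an AUC(0-∞) or half-life value is left out of a summary. SAP 9.3.2 lists the PK parameters and summarizes them descriptively.

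**The concern.** Two things stand out. First, the introduction leaves exclusion open, while step 2e is written as an instruction. Two analysts could treat the same flagged Cmax differently and each cite the SAP.

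Second, this crossover is planned for 30 completers with up to 36 enrolled (SAP 7), and every subject is due both doses. The branch for six or more values is therefore the one that will apply, and it is the branch that does not ask for the comparison with and without the value.

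A 3 SD rule will sometimes flag a perfectly valid value. Removing it narrows the reported SD and geometric CV of exposure. PK in the elderly is a secondary objective reported only through such summaries, so understated variability would be the harm.

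**Working it through.** The plan gives no figure for this point. The check has two parts: the texts side by side, then the size of the effect.

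**Texts**

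1. *Optional or mandatory.* The introduction stands above all the sub-headings that follow and makes both the use of the procedure and the resulting exclusion a matter of scientific judgment. Step 2e is the outcome line of a test inside that procedure. Read in this order, 2e says what the test concludes and the introduction says how far that conclusion binds.
2. *When both results are shown.* There are four cases:
   - within a profile, criterion met: exclusion allowed, no two-way report;
   - within a profile, criterion not met: two-way report;
   - between profiles, fewer than six values, no reliable test: two-way report;
   - between profiles, six or more values, objective test available: test result, no two-way report.

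   The pattern is consistent. Where an objective criterion exists it is applied and documented; where none exists both results are shown.

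**Size of the effect**

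Inputs: n = 30 to 36 values per dose (SAP 7). The assumptions are log-normal data with no true outlier, every set tested and every flag acted on. The SAP prescribes neither of the last two, so the results are upper bounds.

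1. Chance that a given valid value lies beyond 3 SD of the others: 2 × P(t with n − 2 df > 3/√(1 + 1/(n − 1))).
   - n = 30: cut-off 3/√(1 + 1/29) = 2.95 on 28 df, probability 0.00636.
   - n = 36: cut-off 3/√(1 + 1/35) = 2.96 on 34 df, probability 0.0056.
2. Bound for any value in the set: 30 × 0.00636 = 0.191, and 36 × 0.0056 = 0.202.
3. Simulation of steps 2a to 2e (100,000 sets per n), as a single pass and repeated as the SAP allows:

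| | n = 30 | n = 36 |
|---|---|---|
| Sets losing at least one value | 18.8% | 19.5% |
| Sets losing more than one (repeated) | 3.1% | 3.4% |
| SD ratio in affected sets, single / repeated | 0.860 / 0.837 | 0.881 / 0.859 |
| SD ratio over all sets, single / repeated | 0.974 / 0.969 | 0.977 / 0.973 |

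4. Cross-check of the all-sets ratio at n = 30, single pass: 1 − 0.188 × (1 − 0.860) = 0.974.
5. Yardstick: the relative sampling error of an SD is 1/√(2(n − 1)), which is 1/√58 = 13.1% at n = 30 and 1/√70 = 12.0% at n = 36.
6. On the reported scale, geometric CV = √(exp(s²) − 1). The documents give no CV, so two are assumed, at n = 30. With a true CV of 30%, the mean in affected sets is 25.4% (single) or 24.7% (repeated) instead of 29.8%. With 50%, it is 42.1% or 40.9% instead of 49.7%.

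The loss averaged over all sets is a fraction of the sampling error. In an affected set it is about one standard error.

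**The case for a change.** The best case for a change is this. The introduction does more than make the test optional: it also says that identifying an outlier does not oblige anyone to remove it, and step 2e says the reverse about the same event. The within-profile rule uses permissive wording where discretion is meant, so the stricter verb in 2e does not look like loose drafting. The SAP also treats approval of the final report as approval of the exclusion, without requiring that report to show what the exclusion did to the summary. The remedy looks cheap: a softer verb, and one extra table if a value is removed.

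The difference in wording is real, and an all-values summary beside the trimmed one would be a reasonable courtesy to readers. Neither makes the plan deficient.

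Softening the verb gains nothing. If the introduction governs, the discretion already exists. If 2e governs, the edit adds freedom after the value has been seen, at the one step that is now fixed. It also sits awkwardly with the repetition clause, which aims at a set with every remaining value inside the range; a flagged value that is kept would leave that end point unmet.

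The extra table would hold no new information. Excluded values are documented and parameters are listed, so the concern comes down to a missing summary, not missing data.

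**Conclusion.** No change is needed. Step 2e is worded more strictly than its introduction, but the introduction is naturally read as governing, so this is a drafting slip that analysts can resolve sensibly. Leaving out the two-way report at six or more values follows the section's own logic and is not an oversight.

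The possible effect is confined to the descriptive spread of the PK parameters. At worst, about one clean set in five loses a valid value and the log-scale SD falls by 2.3% to 3.1% averaged over all sets. That rests on log-normal data with no true outliers, on testing every set and on acting on every flag; actual use starts from a value already judged atypical and is discretionary, so the real effect should be smaller. The calculation says nothing about sets that contain an erroneous value, where exclusion may well improve the summary. Complete profiles cannot be removed by this rule, exclusions are on record, and the primary non-inferiority test on systolic blood pressure does not use these data. A sponsor who wished to show the all-values summary alongside could do so without amending the SAP.

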### Reporting of Excluded Values

Individual values excluded as outliers will be documented in the final report. Approval of the final report will connote approval of the exclusion.

### **9.3.2 Pharmacokinetic Statistical Methodology**

The PK parameters will be listed, and summarized using standard descriptive statistics, including estimates of intra-subject variability as appropriate. Arithmetic mean (+/- 1 SD) plasma

concentration profiles, as well as individual subject profiles, will be presented graphically by treatment over time.

## 9.4 Cardiovascular Assessment

### 9.4.1 Cardiovascular Analysis

The primary parameter for the cardiovascular analyses will be peak hourly mean values of SBP, and will be determined using ambulatory blood pressure monitoring (ABPM). For each subject, the mean SBP value will be calculated for each hour within the dosing period. The highest mean value across the 24 calculated means will be considered the peak hourly mean value. Baseline value will be defined as the mean value during the 2 hours pre-dose for each period.

Additional analysis will be performed if warranted upon review of the data.

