#### 3.2. Background

Across the completed Phase 1, 2, and 3 clinical studies, doses of 0.1 to 400 mg of lasmiditan were evaluated in healthy subjects or patients with migraine. Compared with placebo, the most frequently reported lasmiditan treatment-emergent adverse events (TEAEs) included dizziness, paresthesia, somnolence, fatigue, lethargy, and nausea. A majority of these TEAEs were mild or moderate in severity and none led to subject withdrawal. One patient experienced a serious adverse event (SAE) of dizziness that was moderate in severity (lasmiditan 200 mg) (Färkkilä et al. 2012).

In the thorough QT study in healthy subjects, no clinically significant changes in BP, heart rate, or 12-lead electrocardiogram (ECG) were observed at the 100- or 400-mg single-dose levels.

In healthy subjects, peak plasma concentrations of lasmiditan were observed approximately 1.5 to 2.5 hours after a single oral dose ranging from 25 to 400 mg, and the geometric mean terminal half-life was approximately 4 hours. Lasmiditan exhibited dose-linear PK.

Co-administration of lasmiditan with a high-fat diet led to a delay in median time of maximum observed drug concentration (tmax) value by approximately 1 hour and a modest (~20%) increase in lasmiditan maximum observed drug concentration (Cmax), and area under the concentration versus time curve (AUC) values, relative to that under fasted conditions.

Following oral dosing with lasmiditan, up to 11 metabolites were detected in human plasma and urine, including 3 major metabolites (M7, M8, and M18). These metabolites lacked significant pharmacological activity at the 5 HT1F receptor and were generally considered to be pharmacologically inactive. The relative proportions of metabolites to intact lasmiditan remained reasonably constant throughout the oral dose range studied and their PK was approximately linear. The half-life of the metabolites ranged from ~4.5 to 21 hours.

Preliminary PK results from Study LAHA demonstrated that in elderly subjects, exposure to lasmiditan as measured by AUC from zero to infinity was 26% (90% confidence intervals (CIs) 1.03, 1.55) higher than in young subjects following dosing with 200 mg lasmiditan. There was no statistically significant difference in exposure to lasmiditan based on Cmax. The tmax of lasmiditan was similar between age groups. The geometric mean t1/2 was 5.46 and 4.10 hours in elderly and young subjects, respectively.

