Preliminary safety data from Study LAHA show that single doses of 200 mg lasmiditan were well tolerated by 18 healthy elderly and 17 healthy young subjects in this study, with no reported deaths, other SAEs, or discontinuations due to adverse events (AEs). The types of TEAEs reported were consistent with previous studies of lasmiditan in healthy subjects. In elderly subjects, postdose there was a transient elevation in mean supine systolic blood pressure (SBP) and diastolic blood pressure (DBP) between 60 and 90 minutes postdose, with a mean maximum SBP increase of 14.5 mmHg and DBP increase of 3.8 mmHg compared with baseline. The changes in supine vital signs were maximal at approximately 1.5 hours postdose and had returned toward baseline values by the time of the assessment at 3 hours postdose. No such changes were noted in elderly subjects receiving placebo or in young subjects receiving lasmiditan. There were no apparent postdose trends in orthostatic vital signs for any age group.

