### ***6.3.1. Meals and Dietary Restrictions***

Lasmiditan or placebo will be administered after an overnight fast of at least 8 hours. Subjects will be given a snack prior to bedtime. Subjects will abstain from water 1 hour before and after dosing (except for water given with the dose). Subjects may be permitted to consume a light breakfast (e.g. cereal, toast) at 1 hour postdose at the discretion of the investigator; with the exception of this light breakfast, subjects will remain fasting for 3 hours postdose at which time a meal will be served.

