#### **9.4.2.1. Ambulatory Blood Pressure Monitoring**

For each subject, ABPM will be performed according to the Schedule of Activities (Section 2).

Site investigative personnel should be trained on the correct positioning of the ABPM monitor, use of correct cuff size, and monitor calibration prior to the start of the study. Subjects should be trained on the ABPM device on the evening of Day -1 to maximize the collection of valid measurements, and to alleviate any concerns about inconvenience due to the continuous 24-hour monitoring.

The ABPM device should be attached to the subject's nondominant arm and will record ambulatory BP and PR every 20 minutes during awake hours (e.g. 0700 hours to 2200 hours) and every 30 minutes throughout the night (2200 hours to 0700 hours). On Days 1, 3, and 5 when dosing occurs, the BP and PR recording will be initiated approximately 2 hours prior to the planned dosing time and will continue for approximately 26 hours. Subjects will be encouraged to keep the same routine without strenuous activity during the ABPM recording days.

The ABPM device should be removed from each subject prior to their discharge from the CRU.

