A repeated measures analysis will also be conducted in which changes from baseline in hourly mean values of SBP will be analyzed to test whether each dose of lasmiditan (100 mg, 200 mg) is noninferior to placebo at each time point (hour), assuming a noninferiority margin of 10 mmHg. A repeated measures linear mixed-effects model with baseline as a covariate, fixed effects for time point, treatment, period, treatment sequence, and the treatment by time point interaction, and a random effect for subject will be used to conduct the tests at a 1-sided significance level of 0.05. At each time point, LS means and treatment differences (lasmiditan 200 mg – placebo, lasmiditan 100 mg – placebo) will be calculated and presented with their corresponding 95% CIs, from which noninferiority of lasmiditan (100 mg, 200 mg) to placebo will be determined if the upper confidence limit is less than 10 mmHg.

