The following gatekeeping procedure will be used to adjust for multiplicity when conducting the hypothesis tests. The null hypothesis that the difference in mean baseline change between lasmiditan 100 mg and placebo is at least 10 mmHg will first be tested against the alternative hypothesis that this difference is less than 10 mmHg. If the p-value for this test is less than 0.05, then there is significant evidence that lasmiditan 100 mg is non-inferior to placebo and these hypotheses will be re-tested using lasmiditan 200 mg. Otherwise, if the p-value is at least 0.05, then there is no significant evidence that lasmiditan 100 mg is non-inferior to placebo, in which case the null and alternative hypotheses will not be re-tested using lasmiditan 200 mg.

A sensitivity analysis will be performed on subjects who complete all 3 dosing periods. In addition, sensitivity analyses will be conducted where baseline value is the mean SBP value during the 1 hour pre-dose for each period. These analyses will be performed separately on subjects who complete at least 1 dosing period and on subjects who complete all 3 dosing periods. The same mixed-effects model as that was used in the primary analysis will be implemented.

A repeated measures analysis will also be conducted in which changes from baseline in hourly mean values of SBP will be analyzed to test whether each dose of lasmiditan (100 mg, 200 mg) is non-inferior to placebo at each time point (hour), assuming a non-inferiority margin of 10 mmHg. A repeated measures linear mixed-effects model with baseline as a covariate, fixed effects for time point, treatment, period, treatment sequence, and the treatment by time point interaction, and a random effect for subject will be used to conduct the tests at a 1-sided significance level of 0.05. An unstructured covariance structure will be applied. If the model fails to converge, alternative structures shall be examined using Akaike's criteria. At each time point, LS means and treatment differences (lasmiditan 200 mg – placebo, lasmiditan 100 mg - placebo) will be calculated and presented with their corresponding 95% CIs, from which non-inferiority of lasmiditan (100 mg, 200 mg) to placebo will be determined if the upper confidence limit is less than 10 mmHg.

An example of the SAS code that will be used is as follows:

```
proc mixed data=xxx;
  class trtmnt time period seq subject;
  model cardiochg = base time trtmnt period seq trtmnt*time / alpha=0.05 cl ddfm=kr;

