  repeated time / type=un subject=subject;
  random subject;
  lsmeans trtmnt*time / alpha=0.05 cl pdiff=controll('reftrt');
run;
```

where cardiochg is the change from baseline in hourly mean values of SBP, trtmnt is the treatment, seq is the treatment sequence, and reftrt is the reference treatment of the comparison.

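### The hour-by-hour noninferiority model defines its covariance block by subject alone, although each subject has three periods, so the block is singular as written

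*SAP*

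**What the plan says.** **Primary analysis.** SAP 9.4.1 and Protocol 10.3.3.1 average ambulatory SBP by hour and take the maximum: "The highest mean value across the 24 calculated means will be considered the peak hourly mean value". The change from the 2-hour pre-dose mean is tested against 10 mmHg at one-sided 0.05, first for 100 mg and then, if that passes, for 200 mg.

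**Hourly analysis.** Protocol 10.3.3.2 and SAP 9.4.2 add a repeated-measures model for the hourly changes, with baseline, time, treatment, period, sequence, treatment-by-time and a random subject effect. At each hour, noninferiority "to placebo will be determined if the upper confidence limit is less than 10 mmHg", the limit being that of a 95% CI. The SAP says it will "conduct the tests at a 1-sided significance level of 0.05. An unstructured covariance structure will be applied", with other structures compared by Akaike's criterion if the model does not converge. The text does not name the unit within which the covariance applies. Only the example code does: "repeated time / type=un subject=subject", followed by a random subject statement and a one-sided comparison with control (`pdiff=controll`, `alpha=0.05`).

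**Why the early hours matter.** Protocol 3.2 describes the changes in the earlier elderly cohort as "maximal at approximately 1.5 hours postdose and had returned toward baseline values by the time of the assessment at 3 hours postdose".

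**What else covers those hours.** The completer and 1-hour-baseline sensitivity analyses reuse the 24-hour peak. Post-dose supine vital signs are scheduled at 4 h and 24 h and are only summarized. Hourly SBP means are also summarized and plotted, without a test.

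**The concern.** The study exists because of a short rise within about three hours of dosing. The hourly model is the one planned inferential analysis that can place a confidence bound on the lasmiditan-placebo difference in that window. In a crossover, the precision of that bound comes from the variance of the within-subject difference between periods at the same hour, and the coded block misstates exactly that variance.

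If the code is run as written, the fit should break down. Someone would then choose a working specification after the data are available, and the SAP's fallback does not point to the right repair. The level of the hourly test is also open to two readings, so an hour close to the margin could pass under one and fail under the other.

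**Working it through.** **1. The plan's own power.** Inputs from Protocol 10.1 and SAP 7: 30 completers, SD 6.0 mmHg, margin 10, true difference 5, one-sided 0.05. Power = Φ((10 − 5)/SE − 1.645).
- 6.0 read as a per-period SD: SE = 6 × √(2/30) = 1.549; power = Φ(3.227 − 1.645) = 94.3%.
- 6.0 read as the SD of the paired difference: SE = 6/√30 = 1.095; power = 99.8%.

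The stated figure of at least 90% holds either way. It concerns the primary test, which is not in dispute.

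**2. Data structure.** 3 periods × 24 hourly means = 72 records per completer, and 30 × 72 = 2,160 in all. Each time level occurs three times per subject. An unstructured 24 × 24 matrix Σ has 24 × 25/2 = 300 parameters.

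**3. Covariance implied by the code.** With time as the only index and subject as the block, records i and j have residual covariance Σ[time i, time j]. Two records at hour h in different periods get Σ[h,h], the variance itself, so their correlation is 1. With records ordered by period and then hour (J₃ is the 3 × 3 matrix of ones):
- R = J₃ ⊗ Σ, a 72 × 72 matrix of rank at most 24.
- The random subject effect adds σ²·J₇₂, of rank 1, so total rank is at most 25. It stays at 24 when Σ has full rank, because J₃ ⊗ Σ + σ²·J₇₂ = J₃ ⊗ (Σ + σ²·J₂₄). The same identity shows that σ² cannot be separated from Σ.
- For the same-hour difference between drug and placebo periods, variance = Σ[h,h] + Σ[h,h] − 2Σ[h,h] = 0.

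A 72 × 72 matrix of rank 24 has no inverse, so the likelihood is not defined for real data. A numerical check with an arbitrary full-rank Σ gave rank 24 with and without the random effect, and a contrast variance of 0.

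**4. The fallback.** Changing the type leaves the index and block as they are. Under AR(1), two records at the same time level have correlation ρ⁰ = 1. Under compound symmetry they share the diagonal element. The singularity remains.

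**5. Block within subject and period.** R = I₃ ⊗ Σ, and V = I₃ ⊗ Σ + σ²·J₇₂. The numerical check gave rank 72. The same-hour contrast has variance 2Σ[h,h], and σ² is identified from the covariance between periods. There are 30 × 3 = 90 blocks for 300 parameters, so non-convergence is still possible and a fallback is still needed.

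**6. Level of the hourly rule.** No hourly SD is given. Taking 6.0 as an assumption for both readings in step 1:

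| SE (mmHg) | Estimate must be below, one-sided 0.05 | Estimate must be below, two-sided 95% CI | Shift | Power at true 5 mmHg |
|---|---|---|---|---|
| 1.549 | 10 − 1.645 × 1.549 = 7.45 | 10 − 1.960 × 1.549 = 6.96 | 0.49 | 94.3% vs 89.8% |
| 1.095 | 10 − 1.645 × 1.095 = 8.20 | 10 − 1.960 × 1.095 = 7.85 | 0.35 | 99.8% vs 99.5% |

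**7. The p-value.** The primary code sets a test value of 10. The hourly code sets none, so its p-value is against 0 and only the confidence bound addresses the margin.

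**8. The peak test.** In simulation, a uniform 10 mmHg rise at every hour passed the primary test in 4.6–5.7% of trials (nominal 5%). For a rise d at one fixed hour, each subject's maximum moves by between 0 and d, so the mean peak difference cannot exceed d.

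**The case against.** **The gated peak test decides and the hourly model is supportive.** This is the natural reading of both documents, and it stands. Hourly means, changes and plots would still be reported if the model failed.

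**The code is only an example, and a fallback exists.** True, but the code is the only place where the block is defined, and the fallback leaves that definition alone (step 4).

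**The one-sided comparison option already suggests a one-sided 0.05 bound.** This has force. It makes a wording mismatch more likely than a decision to test at 0.025, and it indicates which way to align the text.

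**A reader might go further and infer that the 24-hour peak hides the early rise, so that hours 1–4 should become co-primary.** The documents do not support that. The direction in step 8 holds for a common hour, but its size depends on hourly variability and a placebo day profile that are not given:
- Two simulations with different assumed profiles put the peak difference at 0.8–7.1 mmHg for a true 10 mmHg rise in hour 2 (hourly SD 3–8).
- A 14.5 mmHg rise gave 1.9–7.7 in one set of assumptions (hourly SD 4–8), but 11–14.5 when placebo also usually peaked in that hour or hourly SD was 2.
- If timing differs between subjects, the order can reverse. A 14.5 mmHg individual rise placed at random in hours 1–3 gave a largest mean hourly difference of 4.8–4.9 against a peak difference of 8.6–11.4 (SD 3). Varied timing is plausible: "peak plasma concentrations of lasmiditan were observed approximately 1.5 to 2.5 hours after a single oral dose", and a light breakfast is allowed "at 1 hour postdose at the discretion of the investigator".

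At a true hour-2 difference of 10 mmHg, the peak test passed while an early hour failed in 91–96% of simulated trials. That mostly restates a 5% test at its own margin. At the plan's 5 mmHg, disagreement was 0–6% at hourly SD 4.35–5 and 10–19% at SD 6.3. Requiring hours 1–4 as well would cut power to 81–91% at SD 6.3.

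**Conclusion.** The hourly noninferiority model is misspecified as coded. Its subject block gives same-hour residuals from different periods a correlation of 1, the block is singular, and the fallback does not cure it. This follows from the design and the code and needs no assumption about variability, only that the code is read literally. The documents do not say what a given run would do with it.

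The level of the hourly rule is a smaller inconsistency, worth about 0.35–0.49 mmHg on the bound if the hourly SD matches the plan's 6.0.

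The primary peak test, its gate and its stated power are unaffected. A reader might infer that a primary conclusion of noninferiority is unsafe for the early window, or that the hourly model should become descriptive only. Neither follows. The primary conclusion is about the 24-hour peak, and the documents do not determine how far that differs from the hour-matched difference. Even a correctly fitted hourly model works on means of about three waking readings (the device "will record ambulatory BP and PR every 20 minutes during awake hours"). A rise filling half of one hour would be halved: 14.5 becomes about 7.25 mmHg.

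**What to change.** In SAP 9.4.2:

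1. Define the repeated block within subject and period, for example `subject=subject*period`. Keep the random subject effect for correlation between periods. Say this in the text as well as the code, and apply the same block to every fallback structure.
2. State the hourly rule as follows: a dose is noninferior at an hour if the one-sided 95% upper limit of the hour-matched lasmiditan-placebo difference (the upper limit of the two-sided 90% CI) is below 10 mmHg. Add that the p-value from the comparison-with-control option is against 0 and is not used for this decision.
3. Optionally, as a clarification only, say that noninferiority on the primary test refers to the 24-hour peak and that any failed early-hour bound is reported beside it.

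Keep the primary test, the gate and the 24-hour inferential model. The cost is a few lines of text and code, with no new data, no change in sample size and no effect on the primary test's power. The protocol names no covariance block, so item 1 does not conflict with it. Item 2 sharpens wording that also stands in Protocol 10.3.3.2. Since the SAP supersedes the protocol's statistical section, it can be recorded in SAP 11, which currently declares no changes.
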